10.0 EVALUATION DURING TREATMENT/INTERVENTION

Investigations/Tests	Baseline	At Each Dose of Bavituximab	6 Weeks (+/-5 days) After Initiation of Therapy
Detailed history and physical examination (including height, weight, ECOG, vitals)	X	X (Day 1 of each cycle only)	
Written Informed Consent	X		X (for image guided biopsy)

			of tumor) (phase II only)
EKG	X		
Research Serum	X (phase II only)		X (and every 6 weeks thereafter) (phase II only)
Image-guided biopsy of tumor,	X (phase II only)		X (phase II only, between 5 and 6 weeks)
Hematology (CBC with differential)	X	X	
Liver function tests (including total bilirubin, AST, ALT)	X	X	
Coagulation tests (including PT, aPTT, INR)	X	X	
Urinalysis	X		
Alpha-fetoprotein	X	X	
MRI abdomen with gadolinium or CT Abdomen	X		X (and every 6 weeks thereafter) (phase II only)
Bilateral lower extremity venous duplex	X		X (phase II only)
Viral hepatitis titers (Hepatitis B and C)	X (phase II only)		

Investigations/tests at study exit due to disease progression or toxicity or following completion of the phase I component

- Bilateral venous duplex of lower extremities

- History and physical examination (this will continue every 6 weeks for determination of secondary endpoint of overall survival)
- Laboratory tests: same as required at baseline

10.1 Correlative Studies (Phase II patients only)

Pathology Correlative Studies

A major obstacle to molecularly targeted chemotherapeutic agents has been obtaining relevant tumor tissue to measure the agents' biologic effects on target molecules or cellular pathways within the tumor. The utilization of sequential tumor biopsies to obtain tissue following treatment is well established in breast and colorectal carcinoma. (30) However, sequential tumor biopsies of liver tumors are less established due to a fear of procedural complications. The fear of bleeding events following liver biopsy of HCC appears unfounded and based on anecdotal evidence. A large, multi-institutional trial where patients with advanced chronic hepatitis C underwent sequential liver biopsies demonstrated 16 cases (0.6%) of bleeding following 2740 liver biopsies. There were no deaths from peri-procedural bleeding and a platelet count under 60000 was identified as a risk factor. (31) Two large published series of core needle biopsy of HCC as a diagnostic measure report bleeding events in less than 1% of patients with no reported mortalities. In both series capsular location of HCC was associated with increased incidence of bleeding event. (32,33)

In this study all patients will potentially undergo up to two image-guided (either CT or ultrasound) core needle biopsy of a single site of HCC at baseline (for clinical care) and between five and six weeks after the initiation of bavituximab. In addition to the patients receiving treatment as part of this clinical trial, patients identified from the HCC clinics at UT Southwestern who are initiating sorafenib monotherapy will undergo biopsies at baseline and between five and six weeks after initiation. These biopsies are not mandatory to initiate or continue with therapy and are subject to a separate informed consent. To increase patient safety the following conditions must be met prior to liver biopsy:

- Platelet count $\geq 70,000$
- INR ≤ 1.8
- Target lesion not subcapsular in nature as determined by the participating interventional radiology team
- Sorafenib will be discontinued for a period of 24-48 hours prior to biopsy

The patient will sign the informed consent for participation in research liver biopsy prior to the procedure. The liver biopsy will be performed by radiologists and the ancillary staff of Department of Radiology following the standard clinical protocol, which includes obtaining a separate informed consent for the procedure itself. The core samples will be provided to the surgical oncology laboratory. If a core biopsy is performed as a part of the

patient's clinical care, extra cores will be obtained for surgical oncology laboratory, in addition to the cores necessary for clinical care. All cores will be obtained through the same needle to avoid the need of additional punctures and to minimize associated risks.

We will plan to use this tissue to correlate patient outcome measures with markers of anti-angiogenesis therapy and immune response modulation on patients with matched samples. Specifically, we will perform the following tissue based analysis at baseline and 5 and 6 following initiation of either monotherapy with sorafenib or combination therapy with bavituximab and sorafenib :

- Histologic analysis of cell infiltrate of the tumor (specifically macrophage and T cell, both cytotoxic and regulatory)
- Localization of PS exposure on tumor vascular endothelium
- Markers of immune response including T cell activation assays
- Analysis of angiogenic, hypoxia and RAS/MAPK pathway tissue biomarkers

These tissue-based analyses will be correlated with the primary endpoint of time to progression. The collection of tissue in patients treated with sorafenib alone and with combination of sorafenib and bavituximab will allow us to further define the mechanism of action as it pertains to bavituximab. We believe the liver biopsies provide minimal risk to the patient and will allow us to validate whether the therapy regimen affects intended molecular targets to further elucidate mechanism of action. This will allow us in the future to develop a predictive profile to tailor this regimen in patients who will show the most benefit.

Laboratory Correlative Studies

The kinetics of alpha-fetoprotein and viral hepatitis titers (in those patients with baseline elevation) may serve as an early indicator of response to treatment in patients with advanced HCC. These biomarkers have been associated with response to sorafenib therapy and may serve as a predictive biomarker to treatment outcome with the bavituximab and sorafenib regimen. We plan to conduct an analysis of alfa-fetoprotein and viral hepatitis titer levels as biomarker surrogates of outcome. Specifically, alfa-fetoprotein titers will be drawn at baseline, at 2 weeks after initiation of therapy and every 6 weeks thereafter while still enrolled in the study. Quantitative changes in alfa-fetoprotein will be described for patients where matched samples are available and will be correlated with the primary clinical endpoint of time to progression.

In addition, serum angiogenic and hypoxia biomarkers will be analyzed from serum and plasma samples collected from patients treated with bavituximab and sorafenib and sorafenib alone. Blood will be collected in two separate vacutainer tubes, a red top with no additive and a purple top with EDTA additive.

Quantitative changes in the above biomarkers will be described for patients where matched samples are available and will be correlated with the primary clinical endpoint of time to progression.

The biopsy and serum samples for the above correlative studies will be shipped to Peregrine Pharmaceuticals for the completion of only the listed studies. The samples will be de-identified and shipped with codes only known to the primary investigator. All left over tissue or serum will be destroyed by Peregrine Pharmaceuticals.

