5.0 THERAPEUTIC/DIAGNOSTIC AGENTS

5.1 Bavituximab

IND Number: 109134

Finished Product

Presentation and Composition

Bavituximab is supplied as a sterile, preservative-free solution with 10 mM acetate at pH 5.0 and diluted with 0.9% (w/v) saline (normal saline) to a final volume of 100 mL.

Storage

Bavituximab is stored at 2°C to 8°C. Once diluted, it should be stored at room temperature and used within 8 hours.

Availability and Accountability

Peregrine Pharmaceuticals, Inc in Tustin, CA will provide bavituximab. The pharmacist or designee must keep an accurate accounting of the number of investigational units received from Peregrine, dispensed to patients, and returned to Peregrine during and at the completion of the study. A detailed inventory must be completed for the study medication. The study medication must be dispensed only by an appropriately qualified person to patients in the study. The medication is to be used in accordance with the protocol in patients who are under the direct supervision of an investigator. All unused clinical study medications/treatments will be returned to Peregrine.

Administration

Bavituximab will be administered weekly. Prior to each bavituximab infusion, the patient must be pre-medicated with a steroid and an antihistamine to decrease the risk of an infusion reaction, 250 mg hydrocortisone IV and 50 mg diphenhydramine IV administered 30 minutes prior to infusion will be given.

Infusion preparation and administration are to be performed as follows:

1. Draw up the volume of a vial using a sterile syringe attached to an appropriate needle (a vented spike or other appropriate transfer device may be used). Fill treatment into a sterile glass bottle or plastic IV bag.
2. Using aseptic techniques, repeat procedure until the calculated volume has been put in to the container. Bring the final volume to 100 mL using 0.9% Sodium Chloride Injection, USP.
3. Administer through a low protein binding 0.2-micrometer in-line filter (placed as proximal to the patient as practical).
4. Affix the infusion line and prime it with infusate before starting the infusion. Infuse the solution intravenously over 90 (\pm 10) minutes. No reduction in infusion time will be permitted. Flush the line with normal saline after infusion.

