9.3 Supportive Care Guidelines for Therapy (Bavituximab and Sorafenib)

- Recommended anti-emetics for therapy regimen
 - Bavituximab and sorafenib are minimal risk emetogenic regimens. The anti-emetic regimen is per institution guidelines and typically includes no additional anti-emetic therapy.
- Recommended pre-medication regimen to reduce infusion reactions
 - The recommended pre-medication regimen includes the following prior to bavituximab infusion prior to infusion:
 - Hydrocortisone 250 mg IV on all days of IV therapy
 - Diphenhydramine 50 mg IV on all days of IV therapy

The dose of hydrocortisone may be reduced or omitted where medically indicated (i.e. diabetes).

Concurrent supportive care is not restricted, including the use of narcotics for pain control, anti-emetics or anti-diarrheals. No concurrent chemotherapy, immunotherapy, radiation therapy or chemoembolization is permitted during therapy. Use of epoetin alfa and white blood cell support is permitted at the discretion of the treating physician.

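### The sorafenib-only biopsy comparison in Section 10.1 mixes bavituximab with its premedication and with patient selection, so it cannot define bavituximab's own mechanism

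*Combined protocol and SAP*

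**What the plan says.** **The comparison group.** Section 10.1 states that "patients identified from the HCC clinics at UT Southwestern who are initiating sorafenib monotherapy will undergo biopsies at baseline", with a second biopsy between five and six weeks. These biopsies are optional and need separate consent.

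**The assays.** The same tissue analyses are planned for monotherapy and combination patients. They include "Markers of immune response including T cell activation assays", macrophage and T-cell infiltrate, phosphatidylserine localisation, and angiogenic, hypoxia and RAS/MAPK markers. Serum angiogenic and hypoxia markers are also measured in both groups.

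**The inference.** Collecting tissue from both groups "will allow us to further define the mechanism of action as it pertains to bavituximab".

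**The premedication.** Section 5.1 says "Bavituximab will be administered weekly" and that before each infusion "250 mg hydrocortisone IV and 50 mg diphenhydramine IV administered 30 minutes prior to infusion will be given". Section 9.3 lists "Hydrocortisone 250 mg IV on all days of IV therapy" but adds: "The dose of hydrocortisone may be reduced or omitted where medically indicated (i.e. diabetes").

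**The analysis.** Section 15.2 plans Cox regression of TTP on the correlative parameters. Section 15 does not mention the sorafenib-only patients.

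**The concern.** To say something about bavituximab itself, the two groups should differ only in bavituximab. They differ in at least two other ways: a steroid and an antihistamine come with every infusion, and the groups are selected differently.

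This matters because the mechanism under study is largely immune. Section 3.2.1 proposes monocyte-mediated killing of endothelial cells and, more recently, release of proinflammatory cytokines with dendritic-cell activation. Section 5.1 gives the premedication to reduce infusion reactions, and Section 12.2 counts hypersensitivity and cytokine release among those reactions. The protocol therefore does not treat the premedication as immunologically neutral. If it also shifts the tumour or blood markers, a premedication effect could be read as bavituximab's, or a real bavituximab effect could be hidden.

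**Working it through.** The plan gives no sample size, effect size, error rate or test for this comparison, so there is no figure to reproduce. The check has four steps.

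**1. Premedication exposure before the second biopsy.** Inputs: weekly infusions (5.1), 250 mg hydrocortisone and 50 mg diphenhydramine each time (5.1, 9.3), second biopsy at five to six weeks (10.1). Infusions fall on days 1, 8, 15, 22, 29 and 36. A biopsy at five weeks, before that day's infusion, follows 5 infusions. A biopsy just before six weeks follows 6.

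- Hydrocortisone: 5 × 250 = 1,250 mg to 6 × 250 = 1,500 mg
- Diphenhydramine: 5 × 50 = 250 mg to 6 × 50 = 300 mg
- Sorafenib-only group: 0 mg assigned by protocol

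These totals assume that no infusion is missed and no hydrocortisone dose is reduced or omitted.

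**2. Selection rules side by side.**

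| Rule | Trial patients | Sorafenib-only patients |
|---|---|---|
| Section 6 criteria (Child-Pugh, ECOG, bilirubin, measurable disease, cardiac and thromboembolic history, prior therapy) | Required | None stated |
| Platelets ≥ 70,000 and INR ≤ 1.8 | Required (6.1) | Required to be biopsied (10.1) |
| Lesion not subcapsular; sorafenib held 24–48 hours | Required to be biopsied | Required to be biopsied |
| Sites | UT Southwestern and affiliates, VA-North Texas, UT Austin-Seton (Section 7) | UT Southwestern HCC clinics |
| Sorafenib dosing rule | 4.2.2 and 9.1 | None stated |

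**3. What the contrast estimates.** Let each patient's outcome be the change from baseline to the second sample. Then

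mean change (trial) − mean change (clinic) = B + P + S,

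where B is the bavituximab effect, P the premedication effect, and S the difference in change due to selection. Pairing removes any fixed baseline difference. It does not remove P, because premedication starts after baseline, and it does not remove S, because differently selected patients may change differently. There is one contrast and there are three unknowns.

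**4. Whether adjustment can separate them.** At full dose, cumulative hydrocortisone is 250 mg × number of infusions. Within the trial group it varies only from 1,250 to 1,500 mg, a spread of 250 mg, and that variation is itself variation in bavituximab doses. Between groups the gap is 1,250 to 1,500 mg. Hydrocortisone dose is therefore nearly the same variable as group. Only patients whose steroid was reduced or omitted could separate P from B, and Section 9.3 ties that to medical reasons such as diabetes, so they are not comparable with the rest.

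**Blood timing.** The Section 10 schedule takes research serum at six weeks (±5 days) and every six weeks after. Six weeks is 42 days, and 42 / 7 = 6 whole infusion intervals, so the nominal draw falls on an infusion day. Nothing says whether it precedes that day's premedication.

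**The case against.** The strongest reply has four parts.

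**This is openly exploratory.** The trial is non-randomised, the biopsies are optional, and the mechanism claim is one sentence. A later sentence in 10.1 already speaks of the regimen affecting its targets. This stands, and it limits the weight of the point. A reader might infer that the third secondary objective is compromised. It is not: Sections 1.0 and 2.0 word it as correlation of markers with treatment response, without reference to the sorafenib-only patients.

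**Matched samples are already planned.** True: 10.1 analyses patients with matched samples and describes changes in serum markers. This handles fixed baseline differences but not a co-treatment begun after baseline.

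**The exposure contrast is not absolute.** Also true. A reader might infer that every trial patient receives the full steroid dose and that no clinic patient receives any. Section 9.3 allows reduction or omission, and the documents are silent on other steroid use in clinic patients. The wording in 5.1 (mandatory) and 9.3 (recommended, with exceptions) should be reconciled. Likewise, the absence of entry criteria for clinic patients rests on silence, and the biopsy conditions do align platelets and INR.

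**No document shows that weekly premedication alters tumour infiltrate at five to six weeks.** Correct. That it could do so is an assumption. The point is that the design cannot rule it out. Not all the assays are immune, so the premedication concern is most direct for the infiltrate and T-cell activation work; the selection concern applies to all of them.

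**Conclusion.** The concern holds for the mechanism inference in Section 10.1. As written, a between-group difference reflects the premedicated combination regimen in trial-eligible patients against sorafenib in clinic patients with no stated eligibility. It does not isolate bavituximab.

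The known size is the exposure difference: five or six premedications, 1,250 to 1,500 mg hydrocortisone at full dose, against none assigned by protocol. The bias in any marker cannot be sized. The documents give no marker shift, no variability, no group size and no between-group test, so any false-positive rate would come from an invented analysis.

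The conclusion rests on three assumptions: Section 6 is not applied to clinic patients through some unstated route, most trial patients receive the premedication, and premedication could plausibly move at least some of the markers.

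A reader might go further and infer that the efficacy or safety results are affected. The documents do not support that: TTP, the MTD, the safety analyses and the sample size make no use of the sorafenib-only patients. The change is worth making because patients undergo a research-only second biopsy partly for this question, and 10.1 hopes to build a predictive profile on the results.

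**What to change.** In Section 10.1:

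1. Limit the between-group comparison to sorafenib-only patients who meet the Section 6 criteria.
2. State that the comparison is of within-patient changes from baseline, between groups.
3. Draw research blood before premedication whenever the draw falls on an infusion day.
4. Record the hydrocortisone actually given at each infusion and use it for a descriptive sensitivity look only. It should not be used as a covariate adjustment, since it nearly coincides with group.
5. Word the conclusion as the premedicated combination regimen versus sorafenib, in a non-randomised exploratory comparison, and not as bavituximab's own mechanism.

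Premedication itself is unchanged.

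**Cost.** Mostly wording, plus one item that can be collected at the medication review already held at each treatment visit (9.1). The real downside is fewer sorafenib-only patients in a comparison that already depends on optional biopsies. Items 1 and 2 reduce the selection difference but do not abolish it, and nothing here separates bavituximab from its premedication, which is why item 5 is essential.

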11.0 DOSE-LIMITING TOXICITIES-PHASE I COMPONENT

The phase I component of the study will consist of a traditional 3+3 dose escalation rule with the dose of sorafenib remaining constant and the dose of bavituximab escalating up to 3.0 mg/kg weekly to determine the maximum tolerated dose (MTD) that will be used during the phase II component. Sorafenib has been demonstrated in multiple phase I and II studies in advanced HCC to have minimal toxicity and to be safe, therefore doses will be constant. (13,14) Cohorts of three patients will be assigned to one dose level of bavituximab starting at 0.3 mg/kg weekly. Only the first cycle of therapy (4 doses of bavituximab and 4 weeks of sorafenib constitutes a cycle) will be used to determine dose limiting toxicity (DLT). The patients will be followed for thirty days following the end of the first cycle for adverse events. These adverse events will be submitted to the Data Safety Monitoring Committee for evaluation. During this thirty-day period and beyond patients will be administered sorafenib at the discretion of the treating oncologist. Patients will be enrolled into the next highest drug cohort only after 3 or 6 patients have completed the first cycle of therapy. The number of observed toxicities is counted and the traditional escalation rule applied:

- No toxicity: the next three patients will be assigned to next higher dose level (3.0 mg/kg of bavituximab is the highest dose assigned).
- At least two toxicities: the MTD is exceeded and the phase I component of the trial will be stopped with the next lowest dose to be defined as the MTD that will be used in the phase II component.
- One toxicity: the cohort will be expanded to 6 patients.
 - One DLT within the last six patients: The next cohort of three patients will be assigned to the next highest dose level
 - At least two DLTs within the last six patients: the MTD is exceeded and the phase I component of the trial will be stopped with the next lowest dose to be defined as the dose that will be used in the phase II component.

The Data and Safety Monitoring Committee and investigators as described below will regularly review all adverse events. The study will utilize the Common Terminology Criteria for Adverse Events (CTCAE) version 4.0 for grading of all adverse events related to treatment.

The following will be considered a dose-limiting toxicity:

- Grade 4 neutropenia and thrombocytopenia ≥ 7 days (absolute granulocyte count $< 0.5 \times 10^9/L$)
- platelet count $< 25,000$
- ALT or AST levels \geq grade 3 adverse event for 7 days
- \geq grade 3 adverse event for any non-hematologic toxicity (excluding alopecia and non-premedicated nausea/vomiting) attributable to drug therapy by the definition of definite or probable and not possibly. In the SHARP trial patients in the placebo arm had over a 50% \geq grade 3 adverse event rate due to the comorbidities seen in the patient population with advanced HCC.

